## Background

**Patients need higher doses of high-quality rehabilitation therapy:** Stroke remains a leading cause of human disability. Motor deficits are a substantial contributor to this, particularly in the arm: few patients fully recover from arm weakness after a stroke, with the remainder demonstrating persistent arm impairments that are directly linked to larger activity limitations and participation restrictions, lower quality of life, and decreased well-being. Increasing evidence suggests that intensive activity-dependent therapy can improve outcomes after stroke. However, most patients do not receive intensive therapy for reasons that include difficulty traveling to a provider (particularly in the COVID-19 era), shortage of regional rehabilitation care, and poor compliance with assignments.

The amount of rehabilitation therapy received as part of UC is generally small and inconsistent. During the acute stroke admission, the dose of occupational therapy (OT) and physical therapy (PT) provided to a patient varies widely across hospitals. After discharge from the acute admission, the type, location, and dose of rehabilitation therapy are also highly variable.

This is also true in the outpatient setting, where provision of OT and PT after a stroke remains sparse and inconsistent. A study of 23,413 U.S. patients found that during the first 30 days after discharge from the acute stroke admission, 59% did not see an OT or PT at all. A later study of 6,743 adult stroke survivors in the U.S. found that 67% of patients did not receive any outpatient rehabilitation therapy. Medicare generally pays for very few outpatient OT and PT sessions. Outpatient therapy is provided in an inconsistent way, despite the fact that outpatient therapy after stroke has the potential to improve functional status, survival, and quality of life; and to reduce the risk for several psychological disorders. Furthermore, even when patients can access stroke rehabilitation, the amount of therapy provided in standard of care is limited, averaging just 32 arm movements/session, vastly lower than the 600-924 movements/session deemed necessary in animal studies.

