**The rationale for investigating increased dopamine neurotransmission with intensive rehabilitation therapy:** Dopamine is a neurotransmitter that has a key role in learning, and plasticity, with increased dopamine associated with greater motor learning and motor cortex plasticity and decreased dopamine associated with impaired motor learning and motor cortex plasticity. Dopamine is also important to motivation, action learning, action selection, and in the control of voluntary exercise. Dopamine is also a central component in the limbic reward system, and reward significantly influences long-term motor learning.

Given these well-established roles, dopaminergic drugs have also been investigated for poststroke recovery. One key study that motivates Aim 2 was a randomized, double-blind, placebo-controlled study of levodopa performed in patients who experienced a stroke 3 to 26 weeks prior, were admitted for inpatient rehabilitation, and lacked major depression. A total of 53 patients were randomly assigned to 3 weeks of daily levodopa 100 mg (with carbidopa) or placebo coupled with physiotherapy. This study found that levodopa 100 mg/d combined with physical therapy was significantly better than placebo combined with physical therapy for improving arm and leg motor function at the end of the 3 weeks, measured using the Rivermead Motor Assessment. Motor gains were sustained or improved after an additional 3 weeks. No levodopa-related adverse events were reported.

A more recent study also found that levodopa was safe but, perhaps due to study design issues, did not find a benefit in motor recovery. The Dopamine Augmented Rehabilitation in Stroke trial was a multicenter, randomized, double-blinded, placebo-controlled trial with pragmatic design features that examined 6-weeks of daily carbidopa/levodopa (25/100) given prior to rehabilitation therapy in 593 patients recruited 5-42 days post-stroke who could not walk independently. Levodopa was safe; the main safety finding was that vomiting after study drug administration occurred more often in the levodopa group as compared to the placebo group

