### Statistical Analysis

We will present descriptive statistics by group for the important covariates including age, site, time from stroke to randomization, MEP status, and hours of outside rehabilitation. We will also report compliance, defined as the percentage of the 36 sessions during which patients complete more than half ( $\geq 36$  min) of assigned activities. For all analyses, data not normally distributed will be appropriately transformed.

Primary efficacy analysis will use the Intent-To-Treat population, consisting of all randomized subjects and multiple imputation for missing data. Secondary analysis will examine the Per-Protocol population, defined as all subjects with complete data who complete  $\geq 36$  minutes of assigned activities on  $\geq 30$  of the 36 therapy sessions over no more than 8 weeks. Analyses will be performed using SAS and R software.

Logistic regression will be used to create a propensity score for treatment group using age, time from stroke to randomization, and total hours of outside rehabilitation therapy from Visit 1 to Visit 4 (or Visit 3 when change is to visit 3). Inverse weights based on this score will be used in secondary analyses to compute adjusted change distributions and corresponding p values. The primary analyses will be based on the inverse propensity score weighted (adjusted) change from base. The corresponding unadjusted changes will also be reported as a secondary analysis. Since this is a randomized trial, we expected the primary propensity adjusted and unadjusted results to be similar.

**Aim 1. TR+UC is superior to UC alone:** A 6-week program of TR targeting arm movement added to UC will result in better arm function as compared to UC alone. The primary endpoint is the change in ARAT score from baseline to 1 month after end of therapy (Visit 4).

The mean differences in ARAT score change from Visit 1 (baseline) to Visit 4 (1 month after end of therapy) will be compared on the log scale using an inverse propensity adjusted t test. A similar method will be used for the secondary change from Visit 1 to Visit 3 (end of therapy). We will first compare the combined TR + UC groups versus the UC group (Aim 1) and then compare TR+Sinemet+UC versus TR+placebo+UC under this model. (Aim 2). As a secondary analysis, we will report the corresponding unadjusted results.

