The difference in ARAT score change between [1] the combined TR group and [2] the UC group will be computed and the distributions compared using ANCOVA, adjusting for Visit 1 ARAT score and propensity score. Specifically, this Aim will compare UC vs. the combined two TR groups (TR+Sinemet plus TR+placebo).

Exploratory analyses will examine whether aphasia or neglect affect TR efficacy by determining if the extent of aphasia (Visit 1 LAST score) or neglect (Visit 1 SCT score), respectively, is correlated with change in ARAT score from Visit 1 to Visit 4. We will use a linear regression model with ARAT change as the outcome, and with treatment group, LAST score, and propensity score as predictors in order to assess the association. This will be repeated using SCT score instead of LAST score. Restricted cubic splines will be used to determine whether the relationships of language screening and neglect to ARAT score change are each linear.

An additional exploratory analysis will examine whether results vary according to the actual TR dose (the total number of arm repetitions across the 36 treatment sessions), using similar regression methods. Sex will also be explored: while females may have poorer functional outcomes after stroke, it is unclear whether the same underlying factors predict that sex will also be associated with a poorer response to rehabilitation therapy.

Analyses will be repeated examining a secondary endpoint, BBT, and then using several tertiary endpoints (FMA-UE, CES-D, mRS, NHPT, SIS-ADL, and SIS-hand). The lead secondary endpoint is the BBT, and this will be analyzed using alpha=0.05. The tertiary endpoints are considered exploratory and will be examined without correction for multiple comparisons. The same statistical methods as above will be used except that the dependent measure will be change from Visit 1 to Visit 4 in each of the secondary/tertiary endpoints. An additional analysis will examine mRS as the dependent variable but instead using a shift analysis (ordinal logistic repeated measures regression) of mRS change score from Visit 1 to Visits 3 and 4.

To aid in the interpretation of the above analyses, additional corollary analyses will repeat above but use as the dependent measure change from Visit 1 to Visit 3. This will be done for the ARAT as well as for the FMA-UE, BBT, mRS, and SIS-hand subsection.

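### The propensity score behind the Aim 1 primary analysis includes therapy hours accrued after randomisation, so the weighted result can depart from the intention-to-treat effect

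*Combined protocol and SAP*

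**What the plan says.** All of this is in Sample Size and Statistical Analysis unless noted.

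- The score for treatment group comes from a logistic regression on age, time from stroke to randomisation, and "total hours of outside rehabilitation therapy from Visit 1 to Visit 4 (or Visit 3 when change is to visit 3".
- Its role is stated in two ways. One sentence says "Inverse weights based on this score will be used in secondary analyses to compute adjusted change distributions and corresponding p values". The next says "The primary analyses will be based on the inverse propensity score weighted (adjusted) change from base", followed by "The corresponding unadjusted changes will also be reported as a secondary analysis". The Aim 1 text then names an inverse-propensity-adjusted t test and again calls the unadjusted result secondary. On balance the weighted analysis is primary.
- The Aim 1 groups are also to be "compared using ANCOVA, adjusting for Visit 1 ARAT score and propensity score". The same methods are reused for the secondary and tertiary endpoints and for Aim 2.
- The plan's reassurance is: "Since this is a randomized trial, we expected the primary propensity adjusted and unadjusted results to be similar".
- The Visit 1 section lists randomisation among that visit's events. The primary population is intention-to-treat.

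**The concern.** Randomisation balances, in expectation, what is fixed before assignment. It promises nothing about a variable that accrues over the following weeks, so the expected agreement between weighted and unadjusted results holds only if assignment leaves outside-therapy hours unchanged.

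That could fail. Patients know whether they are receiving TR; under Blinding, only the assessors are said to be blind for this comparison. TR asks for 70 minutes a day, six days a week, for six weeks, which could displace other therapy, and UC patients might seek more of it.

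If hours differ by arm because of assignment, weighting on them removes part of the treatment's consequences or adds a spurious difference. The result is not a clean effect at equal outside therapy either, because recovery can itself drive the hours a patient receives. At stake is the primary estimate: Aim 1 asks for the effect of adding TR to UC in everyone randomised.

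**Working it through.** **1. The plan's own figure.** Inputs from Sample Size: difference 5.7, SD 7.4, two-sided alpha 0.05, 80% power, TR to UC ratio 3:1.

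UC patients = (1 + 1/3) × (1.960 + 0.842)² × 7.4² / 5.7² = 17.6, so 18 UC and 54 TR, 72 in total. SE = 7.4 × √(1/54 + 1/18) = 2.014; 5.7 / 2.014 = 2.83; power is 80.8% by the normal approximation and 79.7% by noncentral t. The stated figure reproduces.

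**2. Bias formula.** Let r be the within-arm correlation of hours with ARAT change, and d the TR minus UC difference in mean hours, in SD units. Balancing hours moves the estimate, in large samples, by about

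bias = −7.4 × r × d.

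Fewer hours under TR (d negative) raises the estimate if r is positive and lowers it if r is negative. If either is zero there is no bias.

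**3. Simulated size under no treatment effect.** Assumed: hours SD 15 h, |r| 0.2 to 0.4, TR taking fewer hours. There were 5,000 trials per cell, analysed as a weighted difference in means with a simple robust SE.

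| TR deficit | Size of d | Formula, points | Simulated bias, points | Type I error |
|---|---|---|---|---|
| 0 h | 0 | 0 | within 0.04 | 4.6–6.5% |
| 5 h | 0.33 | 0.49–0.99 | 0.49–0.97 | 6.8–7.5% |
| 10 h | 0.67 | 0.99–1.97 | 0.90–1.86 | 9.0–13.5% |
| 15 h | 1.00 | 1.48–2.96 | 1.33–2.67 | 12.8–22.1% |

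Weights from age and time from stroke alone gave bias under 0.1 and type I error of 5.8–7.1%, so the 5 h row is not clearly separable from them on type I error.

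**4. Simulated size with a true effect of 5.7.**

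- r = −0.2: 5.2 points and 69% power at 5 h; 4.8 and 61% at 10 h.
- r = −0.4: 5.8 and 80% with no deficit; 4.7 and 62% at 5 h; 3.9 and 46% at 10 h.
- r = +0.4: 7.6 points at 10 h, an overstatement.
- ANCOVA on Visit 1 ARAT plus the score, r = −0.4, 10 h: 3.7 points and 43% power.

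A separate simulation (4,000 trials per scenario) made hours worth +2 to +3 points per SD, so r = 2/7.4 to 3/7.4, or 0.27 to 0.41. With TR 0.25, 0.5 and 1 SD lower on hours, the estimates were 6.2–6.4, 6.6–7.2 and 7.6–8.4. With TR 0.5 SD higher they were 4.8 down to 4.2. The effective UC sample fell from about 16 with no shift to 14 at 0.5 SD and 10.6 at 1 SD. Baseline-only weights kept it near 16.6 and the estimate at 5.6–5.7.

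Hours need not act on recovery for this to happen. With no direct effect but a shared cause (assumed correlation 0.5 with hours, 3 points per SD), the large-sample estimate still moved to 6.5 at 0.5 SD fewer hours and 7.2 at 1 SD.

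**5. A case tied to the Background.** The Background cites a survey in which "67% of patients did not receive any outpatient rehabilitation therapy". Assume 67% have zero hours and the rest average 30 h, SD 15.

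- Mean = 0.33 × 30 = 9.9 h; SD = √(0.33 × (15² + 30²) − 9.9²) = 16.5 h.
- If a quarter of TR therapy users receive none, the deficit is 2.5 h and |d| = 0.15. The formula gives 0.22–0.44; simulation gave 0.18–0.45, type I error 5.5–6.0%, and 73% power at r = −0.4.
- If half receive none, |d| = 0.30. The formula gives 0.44–0.89; simulation gave 0.39–0.82, type I error 6.6–7.6%, and 66% power at r = −0.4.

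The text does not say whether inpatient therapy counts. If it does, fewer patients have zero hours.

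**6. Aim 2 (27 versus 27).** A 5 h difference gave 0.5–1.0 points and type I error of 5.5–6.1%; 7.5 h gave 0.7–1.4 points and 6.6–8.9%.

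**The case against.** The timing of the covariate cannot be disputed. The objections concern size and likelihood.

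- *The large shifts may be unrealistic.* This stands in part. In the mostly-zero-hours case the mean is 9.9 h, so a 10 h TR deficit would mean no outside therapy under TR and 15 h is impossible. Those rows need higher average hours, for instance if inpatient therapy counts. In the anchored case type I error (5.5–7.6%) barely differs from baseline-only weights (5.8–7.1%); the cost there is bias of 0.2–0.8 points and, at r = −0.4, lost power.
- *The sign is unknown.* True. The Background's argument that more intensive therapy helps points to positive r, in which case fewer TR hours would overstate the benefit. Power loss should not be read as the main risk.
- *The planned analysis was not simulated exactly.* True. The log scale and multiple imputation were left out, baseline variables were given no prognostic value, and the robust SE was a choice, since the plan names none.
- *Safeguards exist.* Patients in both TR arms are told to continue usual care, and hours by group and the unadjusted result will be reported. A divergence would therefore be visible, but the compromised analysis would still be primary.
- *Aim 2 is better protected.* It is: both arms receive TR and the pill is blinded. The Background reports that "vomiting after study drug administration occurred more often in the levodopa group as compared to the placebo group" (6% versus 3%), but a 3-point excess in 27 patients is 0.8 patient, far too few to move an arm mean by 5 h.

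**Conclusion.** The concern holds, as a conditional one. A variable measured after randomisation sits inside the analysis that most of the plan makes primary, and the reason given for expecting it to be harmless does not apply to it. Bias needs both an arm difference in hours caused by assignment and a relation between hours and ARAT change; the documents quantify neither. Under the assumed ranges it runs from nothing, through 0.2–0.8 points in the mostly-zero-hours case, to 0.9–1.9 points at two thirds of an SD, in either direction. Aim 2 carries the same flaw at lower risk.

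The case for correction rests on principle rather than on any one simulated figure. If assignment does not affect hours, there is only chance imbalance to correct; if it does, the weights distort the intention-to-treat estimate. Changing the primary analysis after a divergence has been seen would look result-driven, so this should be settled beforehand.

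**What to change.** 1. Remove outside-therapy hours from the propensity score wherever it is used for Aims 1 and 2: the weighted t test, the ANCOVA and the regressions that carry the score. Keep only variables fixed before randomisation.
2. Alternatively, make an unweighted ANCOVA on Visit 1 ARAT, age and time from stroke primary. Its simulated type I error was 4.2–5.5%, with 76–79% power at 5.7 points.
3. If baseline-only weights are kept, specify small-sample inference. With 18 UC patients a simple robust SE gave 5.8–7.1% type I error; power was 77–79%.
4. Keep hours as the by-group description already planned, and label any hours-adjusted treatment comparison exploratory.
5. Reconcile the conflicting sentences so that the weighted analysis is named either primary or secondary.

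The cost is SAP wording. The baseline variables are already collected and N stays at 72. The one thing given up is that the primary result no longer adjusts for outside therapy.

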## Sample Size and Statistical Analysis

### Sample Size

The primary endpoint is the ARAT, the MCID for which is 5.7 points. This study is powered for the Aim 1 analyses, which will compare [1] patients receiving TR (i.e., combining TR+Sinemet with TR+placebo) to [2] patients receiving UC. Based on a randomization distribution of 3:3:2 (TR+Sinemet, TR+placebo, UC), and using a 2-sided alpha of 0.05, this study will have 80% power to detect a mean difference between groups of 5.7 points in the change in ARAT-time, assuming a SD of 7.4 points, with a total of 72 patients: 27 in TR+Sinemet, 27 in TR+placebo, and 18 in UC.

The study is funded to enroll 72 patients. Subject dropout may be as high as 20%, and so when possible additional patients may be enrolled.

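### The primary Aim 1 weighted t test leaves its weights and standard error unstated; at 54 vs 18, raw weights with a pooled variance give a type I error of about 6% to 11%, not 5%

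*Combined protocol and SAP*

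**What the plan says.** All references are to the combined protocol and SAP, under Sample Size and Statistical Analysis.

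- **Primary test.** Under Statistical Analysis, Aim 1, the mean ARAT changes are to be compared, after a log transformation, "using an inverse propensity adjusted t test". The general paragraph above it agrees: "The primary analyses will be based on the inverse propensity score weighted (adjusted) change from base".
- **Conflict.** The sentence directly before that one gives the weights a different role: "Inverse weights based on this score will be used in secondary analyses to compute adjusted change distributions and corresponding p values".
- **Propensity model.** A logistic regression for treatment group "using age, time from stroke to randomization, and total hours of outside rehabilitation therapy from Visit 1 to Visit 4".
- **Design.** Under Sample Size, the trial is planned "using a 2-sided alpha of 0.05", "with a total of 72 patients: 27 in TR+Sinemet, 27 in TR+placebo, and 18 in UC". Aim 1 pools the two TR arms, so it compares 54 with 18.
- **Other Aim 1 analyses.** Unadjusted results are secondary. A further paragraph describes an ANCOVA on Visit 1 ARAT and the propensity score, without ranking it against the weighted test.

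The plan names SAS and R but no procedure. It does not say whether the weights are raw, stabilised or normalised, whether the t test pools the variances, or whether the standard error allows for the score having been estimated.

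**The concern.** Inverse-propensity weights re-create a population in which each arm stands for all 72 patients. That is harmless for the two weighted means. It is not harmless for a pooled-variance standard error, which takes the weights as information: with 3:1 allocation it treats the 18 usual-care patients as carrying as much precision as the 54 TR patients. A standard weighted least-squares t test does this when given raw weights, so it is an ordinary way to carry out the planned sentence.

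At stake is the error rate of the trial's main efficacy claim. If two analysts can follow the text and obtain materially different false-positive rates, the 5% level has not been fixed in advance, and the choice could be made after results are seen.

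**Working it through.** **Inputs from the plan.** 54 vs 18 patients, SD of change 7.4, difference 5.7 points, two-sided alpha 0.05, three propensity covariates.

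**Assumption not in the plan.** The share of variance in ARAT change that the covariates explain (R²), taken from 0 to 0.3.

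**1. The plan's own figure.** The unweighted standard error is 7.4 × sqrt(1/54 + 1/18) = 7.4 × 0.272 = 2.01 points. Then 5.7/2.01 = 2.83, and power = Φ(2.83 − 1.96) = 80.8% (79.7% with the t distribution). The stated N = 72 and 80% reproduce, but for an unweighted comparison.

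**2. Pooled standard error with raw weights.** Raw weights average 72/54 = 1.33 in TR and 72/18 = 4 in UC, so each arm's weights sum to about 72.

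- Pooled weighted variance, in units of SD²: (53 × 1.33 + 17 × 4)/70 = 1.981.
- Standard error: sqrt(1.981 × 2/72) = 0.235 SD.
- Ratio to the true value: 0.235/0.272 = 0.86, about 14% too small.
- Where it goes wrong: the UC mean is given variance 1.981/72 = 0.028 SD² instead of 1/18 = 0.056.
- False-positive rate from this alone, with constant weights: 2 × [1 − Φ(1.96 × 0.862)] ≈ 9%.

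This step needs no assumption about R².

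**3. Simulation with an estimated score.** Null effect, 54 vs 18, three covariates independent of arm, logistic score refitted in every trial, 10,000 trials per setting unless noted. Entries are type I error at nominal 5%.

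| Handling | R² = 0 | R² = 0.3 |
|---|---|---|
| Raw weights, pooled variance | 11.3% | 6.1% |
| Stabilised weights, pooled variance | 6.3% | 3.0% |
| Weighted, unequal variances | 6.5% | 3.0% |
| Survey-type robust SE | 6.6% | 3.1% |
| Sandwich allowing for the estimated score | 7.5% | 6.7% |
| Bootstrap refitting the score (800 trials) | 8.0% | 5.6% |
| Permutation refitting the score (600 trials) | 5.5% | 5.5% |
| Unadjusted t test | 5.2% | 5.3% |
| ANCOVA, the three covariates entered directly | 5.1% | 4.6% |
| ANCOVA on the propensity score (600 trials) | 5.0% | 2.7% |

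Separate repeats of the first row, with 5,000 to 6,000 trials each, gave 10.3-11.5% at R² = 0, 9.1-9.6% at 0.1, 7.5-7.9% at 0.2 and 6.0-6.5% at 0.3. At R² = 0.5 the first row falls to 3.2%.

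**4. Why R² matters.** Weighting by an estimated score removes chance imbalance, so the estimate becomes less variable when the covariates are prognostic: its empirical SD was 1.82 points at R² = 0.3, against 2.01 unweighted. A standard error that ignores this stays too wide, hence the conservative 3%.

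**5. Scope.** At 27 vs 27, the Aim 2 comparison, raw weights with pooled variance gave 5.9% at R² = 0 and 2.1% at R² = 0.3 (5,000 trials). The marked inflation comes from the 3:1 allocation and so concerns Aim 1.

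**The case against.** The best defence is that the plan never says the weights will be raw. An analyst who normalises within arm and uses an unequal-variance or robust standard error gets about 6-7% down to 3%, which is close to nominal or cautious. The plan also expects weighted and unweighted results to agree, reports the unadjusted comparison, and describes an ANCOVA, so a result seen only in the weighted test would be visible. The simulation omits the log scale and the multiple imputation, so its percentages are illustrative.

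Much of this stands, and it limits the point. It does not remove it: agreement of the two estimates says nothing about their standard errors, supporting analyses do not protect the primary p value, and the text allows the raw-weight version as readily as the normalised one.

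Three stronger readings are tempting, and the documents do not support them.

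- **That no valid standard error exists.** It is unspecified, not non-existent. The permutation test that refits the score held 5.5%.
- **That the error rate runs from 3% to 26% depending on software.** The 26% needs weights read as patient counts, turning 72 patients into about 144, which the plan does not call for. The 3% needs R² near 0.3, so the two ends also differ in an assumption that the plan does not supply.
- **That rescaling or a robust standard error achieves nothing.** Either removes most of the inflation.

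**Conclusion.** The concern holds as a gap in specification with a real consequence. The primary Aim 1 test is named without a weight form or standard error, and adjoining sentences disagree on whether the weights belong to primary or secondary analysis. One ordinary execution, raw weights with pooled variance, has a standard error about 14% too small and a type I error of about 10-11% at R² = 0, falling to about 6% at R² = 0.3. The 14% is algebra with weights at their arm averages. The percentages rest on the assumed R², on normal covariates independent of arm, and on untransformed, complete data. If the covariates were much more prognostic (R² = 0.5), the same test would be conservative. The matter should be settled before unblinded analysis; it does not call the sample size or the design into question.

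**What to change.** In Statistical Analysis, delete the sentence that puts the inverse weights in secondary analyses together with the one that makes them primary, and replace the Aim 1 test with one statement: the primary analysis is an ANCOVA of ARAT change on arm (combined TR vs UC), with Visit 1 ARAT, age and the stroke-to-randomisation interval entered directly, two-sided 5%, combined across imputed data sets by the usual rules. State the scale; the sample size is set in ARAT points. Entering the covariates directly is preferable to the ANCOVA on the propensity score, which gave 2.7% at R² = 0.3. The simulated ANCOVA used three covariates and no Visit 1 ARAT; adding a baseline measure does not disturb the level of an ANCOVA in a randomised comparison.

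If the weighted difference is kept as a supporting analysis:

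- build the score from baseline covariates only; outside-therapy hours accrue after randomisation, and if they differed by 0.5 SD between arms at R² = 0.3 (both assumed) the estimate would shift by about 1.1 points whatever standard error is used;
- normalise the weights within arm;
- name the standard error, or use a re-randomisation test that refits the score at each draw, follows the actual allocation scheme and states how results are pooled over imputations;
- rule out a pooled t test on raw weights.

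The cost is analysis wording and a short program, with no extra patients or data. The downside is that the primary p value may be less favourable than under raw weights.

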**Aim 2. TR+Sinemet is superior to TR+placebo:** Among patients randomized to TR, gains in arm function will be greater in those who take Sinemet (25/100) prior to daily TR, as compared to patients who take placebo prior to TR.

The above analyses will be repeated but instead comparing patients randomized to [1] TR+Sinemet vs. [2] TR+placebo.

**Aim 3. Less CST injury and higher dopamine polygene score predict better recovery of arm function:** Across all subjects, change in arm function will be highest in those with lower % CST injury and in those with higher dopamine polygene scores. These relationships will remain significant when examining only patients randomized to TR. The drug X gene score interaction term will be significant such that the slope of arm gains in relation to the polygene score will be smaller (less steep) in those receiving Sinemet.

**H3A:** Using linear regression, we will test whether lower % CST injury predicts higher change in ARAT score from Visit 1 to Visit 4, after controlling for baseline ARAT score and clinical measures (age, time from stroke to randomization, and total hours of outside rehabilitation therapy from Visit 1 to Visit 4). Primary analysis will examine all enrollees. Secondary analysis will examine this relationship separately for patients randomized to one of the two TR groups, while tertiary analysis will examine this separately across all three treatment groups.

Restricted cubic splines will be used to determine if the effect of continuous covariates such as age are linear. A linear model that includes individual clinical measures will be used rather than propensity adjustment so that the effect of % CST injury can be compared to the effects of the other covariates. This approach also allows us to test the hypothesis that % CST injury predicts ARAT gains beyond what can be learned from clinical variables alone.

**H3B:** We will test whether higher dopamine polygene score predicts higher change in ARAT score from Visit 1 to Visit 4, after controlling for the same covariates as in H3A. Analyses will follow those described in H3A.

Secondary analysis will repeat H3A and H3B using change in BBT from Visit 1 to Visit 4 as the dependent measure. Tertiary analyses will repeat these methods focusing on change in FMA-UE, CES-D, mRS, NHPT, SIS-ADL, and SIS-hand scores.

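### The ANCOVA for Aims 1 and 2 adjusts for a fitted propensity score rather than for age and time from stroke, which forgoes some power if those covariates are prognostic, and the score contains post-randomisation therapy hours.

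*Combined protocol and SAP*

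**What the plan says.** The Statistical Analysis section of the combined protocol and SAP introduces the score: "Logistic regression will be used to create a propensity score", built "for treatment group using age, time from stroke to randomization, and total hours of outside rehabilitation therapy from Visit 1 to Visit 4" (to Visit 3 when that is the endpoint visit). Two of the three inputs are fixed at randomisation. The third accrues after it.

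The score is then used in two ways. Its inverse weights feed a weighted t test of ARAT change on the log scale. The section calls the weighted analysis primary, although one sentence there places the weights in secondary analyses. Separately, under Aim 1, the change is to be "compared using ANCOVA, adjusting for Visit 1 ARAT score and propensity score". The role of this ANCOVA is not stated, and neither is a variance estimator. Aim 2 repeats the Aim 1 analyses for Sinemet against placebo, and BBT and the tertiary endpoints use the same methods.

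For hypothesis H3A under Aim 3 the plan takes the other route: "A linear model that includes individual clinical measures will be used rather than propensity adjustment".

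The Sample Size section makes no allowance for covariates: "using a 2-sided alpha of 0.05, this study will have 80% power to detect a mean difference between groups of 5.7 points", "assuming a SD of 7.4 points", "with a total of 72 patients: 27 in TR+Sinemet, 27 in TR+placebo, and 18 in UC".

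**The concern.** Under randomisation, a propensity score fitted to baseline covariates describes chance imbalance between the arms. Conditioning on it moves the treatment estimate to nearly where direct adjustment would put it. But a score built to predict arm is a poor predictor of outcome, so much of the outcome variation due to age and time from stroke stays in the residual. The ordinary ANCOVA standard error is computed from that residual and overstates the sampling variation of the estimate. Intervals are then wider than they need be and the test rejects too seldom.

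The hours raise a different problem. Outside therapy received after randomisation may depend on the arm, so a score containing it need not reflect chance alone. It can become collinear with arm, which makes the estimate itself less precise. Conditioning on a variable that treatment may affect can also bias the effect.

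At stake is precision in a comparison with 18 UC patients, in a trial funded for 72 with possible dropout of 20% not built into that number.

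**Working it through.** **Inputs.** From Sample Size: difference 5.7, SD 7.4, two-sided alpha 0.05, 54 TR vs 18 UC (Aim 1), 27 vs 27 (Aim 2). The documents give no R² of age and time from stroke for ARAT change, so 0 to 0.30 is assumed. The nearest figure, 17.6% in the Background, comes from a multivariable model of arm motor gains, chosen after screening 43 clinical measures in another trial population. It is one point in the range, not an estimate for this trial.

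**Step 1: the plan's own figure.** With 3:1 allocation, n(UC) = (1 + 1/3) × (1.960 + 0.842)² × (7.4/5.7)² = 1.333 × 7.85 × 1.685 = 17.6, rounded up to 18, so 54 + 18 = 72. The SE is 7.4 × √(1/54 + 1/18) = 2.014, and 5.7/2.014 = 2.83. Power is 80.8% (normal) or 79.7% (t). The figure reproduces.

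**Step 2: a ceiling on the excess.** With direct adjustment the SE is about 2.014 × √(1 − R²): 1.91, 1.83 and 1.69 at R² 0.10, 0.176 and 0.30. If the score removed none of the prognostic variation from the residual, the SE would be too wide by 1/√(1 − R²): 5%, 10% and 20%. In practice the score absorbs part of it, so simulation is needed.

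**Step 3: simulation, Aim 1.** 4,000 trials per setting, total SD 7.4, complete data, raw scale, ordinary model SEs. Visit 1 ARAT and hours are taken as non-prognostic, and hours are equal between arms. Planned model: arm, Visit 1 ARAT, and a score from age, time and hours. Direct model: arm, Visit 1 ARAT, age, time.

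| R² (assumed) | Planned: model SE / true SD (null) | Type I error | Power, planned | Power, direct |
|---|---|---|---|---|
| 0 | 2.06 / 2.04 | 4.7% | 76.9% | 77.9% |
| 0.05 | 2.05 / 1.97 | 4.3% | 78.3% | 80.1% |
| 0.10 | 2.04 / 1.98 | 4.6% | 79.3% | 82.6% |
| 0.176 | 2.01 / 1.89 | 3.5% | 80.1% | 84.2% |
| 0.30 | 1.97 / 1.75 | 2.5% | 84.9% | 90.8% |

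Monte Carlo error is about 0.6 points on each power figure and about 1/√8000 = 1.1% on each true SD. Over separate runs the excess width is about 3-5%, 5-6% and 11-14% at R² 0.10, 0.176 and 0.30. Direct adjustment is calibrated: at R² 0.30 its model SE is 1.72 against a true SD of 1.73, with type I error 4.6%.

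**Step 4: Aim 2 (27 vs 27).** Power, planned then direct, in the same R² order: 74.9% and 75.7%; 76.2% and 78.5%; 79.1% and 81.8%; 80.3% and 85.5%; 82.9% and 89.6%.

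**Step 5: how much is due to the score form.** In Aim 2 at R² 0.176, a score from age and time alone gives 82.5% power. Adding hours to that score gives 80.3%. Direct age and time give 85.5%. Of the 5.2 points, 3.0 come from using a score and 2.2 from having hours in it.

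**Step 6: hours that differ by arm (Aim 1, R² 0.10).**

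| Arm difference in hours (assumed) | Planned | Direct age, time | Direct age, time, hours |
|---|---|---|---|
| 0.5 SD | 75.9% | 81.7% | 79.2% |
| 1 SD | 69.5% | 81.9% | 74.3% |

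At 1 SD the estimate itself is more variable (true SD 2.20 against 1.95), so this loss goes beyond an overstated SE. Because hours were simulated as non-prognostic, these runs show lost power only and do not measure bias.

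**The case against.** The case on the other side is substantial.

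- **Not the named primary analysis.** A reader might infer that the primary test loses this precision. The documents do not support that: the weighted t test on the log scale is called primary, and the figures here concern the ANCOVA on the raw scale. This stands.
- **No shortfall against the stated power.** A reader might infer that the 80% is wrong. It is not. It assumes no covariate gain, and what is forgone is a gain above it. Compared with adjusting for Visit 1 ARAT alone (78-80% power in Aim 1), the planned model loses 1 to 2 points at R² 0 to 0.05, is level at 0.10, and gains 2 to 6 points at 0.176 to 0.30. This stands.
- **The size is conditional.** A reader might infer that the standard errors are too wide whatever the data. At R² = 0 they are not. Two covariates may well explain less than the 17.6% of a broader model, and time from stroke is limited here to 30 days. At the low end the effect is small. This stands.
- **The variance estimator matters.** One that allows for the estimated score would remove most of the excess. This stands in principle, but the plan names none.
- **Aim 3 is not a contradiction.** The plan gives a reason for direct entry there: to compare the effect of corticospinal tract injury with those of the other covariates. So the contrast shows only that direct entry is feasible with the same data.

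None of this gives a reason to prefer the score. Direct entry had no lower power at any R² tested, including 0.

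**Conclusion.** The point holds as an efficiency issue in a prespecified treatment-effect model whose role is unstated. If age and time from stroke explain 10%, 17.6% or 30% of the variance in ARAT change, and ordinary model SEs are used, the ANCOVA standard error is about 3-5%, 5-6% or 11-14% too wide. Power forgone against direct adjustment is then about 3, 4 and 6-7 points (about 5 rather than 4 for Aim 2 at 17.6%). The error is conservative: it does not inflate type I error.

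The post-randomisation hours are the more serious part. With an assumed arm difference of 0.5 or 1 SD and R² 0.10, separate runs put power at about 76-77% or 70%, against about 82% with age and time alone. The possible bias is unquantified, because the documents say nothing about how hours will differ between arms or relate to outcome. All these sizes rest on assumed R² values, complete data and the raw ARAT scale.

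**What to change.** In the Aim 1 ANCOVA, and by reference in Aim 2, replace the propensity score with age and time from stroke to randomisation as separate terms, alongside arm and Visit 1 ARAT. For BBT and the tertiary endpoints, use the endpoint's own Visit 1 value where one is collected. The Schedule of Events first places the SIS subsections in week 2 or shortly after discharge home, so those two have none.

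State explicitly that outside therapy hours accrued after randomisation are left out of this model. State whether the ANCOVA or the inverse-weighted t test is primary, and reconcile the sentence that places the weights in secondary analyses.

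Cost: SAP wording and one more model degree of freedom (two covariate terms in place of one score). No new data are needed.
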